### **Figure 2**

## Criteria for Evaluation

### ***Primary Efficacy Endpoint***

- The primary endpoint is the baseline-adjusted number of diurnal Level 2 hypoglycemia events (ADA, <54 mg/dL) as measured by CGM and defined as the number of events captured by CGM with glucose measures <54 mg/dL during diurnal hours (8am-10pm) within each treatment period divided by number of days for a given treatment period, then normalized to duration of 14 days. The baseline-adjusted number of diurnal Level 2 hypoglycemia events during 14 days of avexitide treatment (Treatment Periods 1 and 2) and 14 days of standard of care treatment (Run-In Period) will be calculated and examined in a mixed-effect model, including treatment, treatment sequence, treatment period, and surgery type stratum (RYGB vs. Others) as fixed effect, and subject-within-sequence as random effect. The least squares (LS) mean, the standard error (SE), the 2-sided 95% confidence interval (CI), and the p-value will be derived from the mixed-effect model for each active treatment. No multiplicity adjustment is planned, and the primary endpoint will be evaluated through the nominal p-values. P<0.05 is considered statistically significant.

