## Study Schedule

The screening period comprises:

- Visit 1 (Zoom): Informed Consent, review of medical history, hypoglycemia questionnaire, concomitant medications, assessment of preliminary eligibility
- Visit 2 (Zoom): training on patient eDiary, glucometer use, and Dexcom G6PRO application and activation. Participants begin 14-day Run-In Period
- Visit 3 (Zoom): Check in with patient.
- On day 10 of the Run-In Period, participants place a new Dexcom G6PRO sensor.
- Visit 4 (SHC): On day 14 of the Run-In Period, participants go to SHC for a urine pregnancy test, an ADA draw, and CMP as applicable then consume a standardized liquid mixed meal over 10 minutes, with fingerstick glucose checks every 30 minutes for a total of 180 minutes. Eligible participants are then enrolled, randomized and dispensed study drug.

Enrolled participants will be randomized 1:1 to one of 2 avexitide dosing regimen orders, and will be trained on study medication injection procedures. Avexitide should be injected subcutaneously either once daily in the morning, or twice daily; once in the morning and the second daily dose approximately 12 hours later. During once daily administration (avexitide 90 mg QD), morning dosing will occur at least 60 minutes prior to the first morning meal. During twice daily administration (avexitide 45 mg BID) morning dosing will not be relative to the timing of the first meal of the day. Throughout, patients will follow currently accepted dietary guidelines for treatment of PBH.

- Visit 5 (Zoom): Participants are trained on study drug injection; initiate Treatment Period 1. Place new Dexcom G6PRO device.
- Day 10 of Treatment Period 1: Participants place a new Dexcom G6PRO device.
- Visit 6 (SHC): On day 14 of Treatment Period 1 participants have a PK and an ADA draw, have their final Treatment Period 1 study drug injection and 90 minutes later consume a standardized mixed meal over 10 minutes, with fingerstick glucose checks every 30 minutes for 180 minutes. Participants are dispensed new study drug and initiate a 2-day washout period.
- Day 4 of Treatment Period 2: Participants place a new Dexcom G6PRO device.

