- Visit 7 (SHC): On day 14 of Treatment Period 2 participants have a PK and an ADA draw, have their final Treatment Period 2 study drug injection and 90 minutes later participants consume a standardized mixed meal over 10 minutes, with fingerstick glucose checks every 30 minutes for a total of 180 minutes. Participants then remove their Dexcom sensor/transmitter and return their used/unused study drug vials.

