### **Blinded Continuous Glucose Monitoring (CGM)**

During the Run-In phase, a Dexcom Mobile G6 Pro Continuous Glucose Monitoring System in blinded mode (i.e., the CGM device) will be issued to potential study participants. Each participant will be trained on its use in accordance with the manufacturer's instructions. Written instructions for CGM use and maintenance will be provided. The instructions will, if necessary, be repeated at site visits. The data from CGM will be downloaded after Run-In and at the end of each 14-day period for enrolled subjects. Each device will be blinded for use during the study. The Dexcom Mobile G6 Pro CGM System must be removed before magnetic resonance imaging (MRI), computed tomography (CT) scan, or high-frequency electrical heat (diathermy) treatment.

[figure not shown]

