### ***Secondary Endpoints***

The secondary endpoints include the following:

- Rate of Level 2 hypoglycemia, defined as number of distinct episodes of Level 2 hypoglycemia (SMBG glucose <54 mg/dL), divided by number of days for a given treatment period, then normalized to duration of 14 days.
- Rate of Level 3 hypoglycemia (severe hypoglycemia), defined as the number of severe events during each treatment period characterized by altered mental and/or physical functioning that requires assistance from another person for recovery, divided by number of days for a given treatment period, then normalized to duration of 14 days. This applies regardless of whether a patient actually receives external assistance. Since the categorization of a severe hypoglycemia event can be subjective, particularly in cases where severe neuroglycopenic symptoms/signs occurred and external assistance was needed but was not received, all potential qualifying severe hypoglycemia events will be adjudicated by the principal investigator.
- Percent diurnal time <54 mg/dL, defined as the percentage of CGM values <54 mg/dL during daytime hours (8am-10pm) within each treatment period, normalized to 14 days.
- The magnitude of postprandial hypoglycemia, defined as the glucose nadir as measured by fingerstick glucose occurring within 3 hours of standardized liquid meal consumption. The plasma glucose nadir obtained during avexitide plus standard of care (Treatment Periods 1 and 2) will be compared to during standard of care (Run-In). Particularly, the baseline-adjusted plasma glucose nadir will be calculated for each patient and evaluated.

Secondary endpoints will be analyzed in the same manner as the primary efficacy endpoint.

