### ***Exploratory Endpoints***

- QoL as measured by SF 36 v2, EQ-5D, HSF-II, and HCS.
- Rate of hypoglycemia, defined as the number of distinct episodes of SMBG glucose <70 mg/dL divided by number of days for a given treatment period, then normalized to duration of 14 days.

- Percent time >250 mg/dL, defined as the percentage of CGM values >250 mg/dL during each treatment period, normalized to 14 days
- Percent nocturnal time <54 mg/dL as measured by CGM, defined as the percentage of CGM values <54 mg/dL during nocturnal hours (12am-6am) within each treatment period, normalized to 14 days.
- Number of nocturnal Level 2 hypoglycemia events (ADA, <54 mg/dL) as measured by CGM and defined as the number of events captured by CGM with glucose measures <54 mg/dL during nocturnal hours (12am-6am) within each treatment period divided by number of days for a given treatment period, then normalized to duration of 14 days.

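### CGM event counts are divided by days in the period rather than by CGM-observed time, so lost sensor time counts as event-free; three CGM percentages also carry a needless 14-day scaling

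*Combined protocol and SAP*

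**What the plan says.** All references are to the combined protocol and SAP.

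- **Primary Efficacy Endpoint.** Events detected by CGM below 54 mg/dL are counted "during diurnal hours (8am-10pm) within each treatment period divided by number of days for a given treatment period", and the result is scaled to 14 days. It is baseline-adjusted and compared with the Run-In in a mixed-effect model.
- **Exploratory Endpoints.** Nocturnal Level 2 events are counted "during nocturnal hours (12am-6am) within each treatment period divided by number of days for a given treatment period", with the same scaling.
- **Secondary Endpoints.** The SMBG and Level 3 rates use the same denominator, so it is not specific to CGM.
- **Blinded Continuous Glucose Monitoring (CGM).** On data handling this section says only: "The data from CGM will be downloaded after Run-In and at the end of each 14-day period for enrolled subjects". It also requires removal of the device before MRI, CT or diathermy. Neither it nor any other section defines a valid day, a minimum wear time or a rule for missing CGM data.
- **Study Schedule.** At the Visit 5 entry: "initiate Treatment Period 1. Place new Dexcom G6PRO device". At the end of Visit 7, on Day 14 of Treatment Period 2: "Participants then remove their Dexcom sensor/transmitter and return their used/unused study drug vials". Appendix A also puts the first Run-In sensor on Day 1.
- **Percent-time endpoints.** Three are defined as percentages of CGM values and then normalized: "the percentage of CGM values <54 mg/dL during daytime hours (8am-10pm) within each treatment period, normalized to 14 days" (secondary), "the percentage of CGM values >250 mg/dL during each treatment period, normalized to 14 days" and "the percentage of CGM values <54 mg/dL during nocturnal hours (12am-6am) within each treatment period, normalized to 14 days" (both exploratory).

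**The concern.** The numerator and denominator of the two event counts measure different things. The numerator can grow only while a sensor is recording inside the clock window. The denominator keeps growing whether or not a sensor is recording. Hours lost to sensor failure, a late replacement, removal for imaging or early removal therefore enter as observed hours with no hypoglycemia.

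This would matter little if loss were the same in every period and results were read as ratios. The primary result, however, is a baseline-adjusted count from an open-label trial of up to 20 participants, with the Run-In as the comparator. More loss on treatment than in Run-In makes the drug look better; more loss in Run-In hides an effect. Equal loss leaves the ratio unchanged but shrinks the absolute difference.

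The percent-time endpoints have the opposite fault. They already divide by observed CGM values, so a further scaling to 14 days has no purpose.

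**Working it through.** The plan states no event rate, coverage, effect size or power, so there is no figure of its own to reproduce. The windows and visit days below come from the documents; clock times, event rates and loss rates are assumptions.

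**1. Windows.** Diurnal: 14 h x 14 d = 196 h. Nocturnal: 6 h x 14 d = 84 h.

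**2. Understatement.** If a share f of the window is lost and loss is unrelated to events, the expected count is true rate x (1 - f), while the denominator stays at 14 days. The relative error is -f. One lost day is 14/196 = 7.1%; one lost night is 6/84 = 7.1%. At 90% coverage, 10 true events per 14 days are reported as 9.0; at 80%, as 8.0.

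**3. Loss built into the schedule (diurnal).**
- Removal on Day 14 of Period 2 at hour h loses (22 - h)/196: 11/196 = 5.6% at 11am, 7/196 = 3.6% at 3pm. No nocturnal hours are lost.
- Placement on Day 1 of Run-In and of Period 1 at hour h loses (h - 8)/196: 1/196 = 0.5% at 9am, 7/196 = 3.6% at 3pm.

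**4. Effect on the difference from Run-In.** With true rates R (Run-In) and T (treatment), the expected reported difference is T(1 - fT) - R(1 - fR) = (T - R) + R·fR - T·fT. Take R = 8 and T = 4, so the true difference is -4.0.

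*Schedule only*, with fT averaged over the two treatment periods because the sequences are allocated 1:1:
- Lowest: 8 x 1/196 - 4 x (7/196 + 11/196)/2 = -0.14.
- Highest: 8 x 7/196 - 4 x (1/196 + 7/196)/2 = +0.20.
- With both placements at the same hour: -0.08 to +0.14.

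*Larger loss*: 20% of participants lose 5 of 14 days, so the mean f is 0.2 x 5/14 = 0.0714.

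| Where the loss falls | Reported difference | Error |
|---|---|---|
| Treatment only | -4 - 4 x 0.0714 = -4.29 | 7% too large |
| Run-In only | -4 + 8 x 0.0714 = -3.43 | 14% too small |
| Both | -4 + 8 x 0.0714 - 4 x 0.0714 = -3.71 | 7% too small |

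Dividing by observed hours gives -4.0 on average in all three rows.

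**5. False-positive rate under no drug effect.** The simulation used n = 20, gamma-distributed participant rates (shape 2), Poisson counts, a paired t-test at two-sided 5%, 20,000 trials, and the same 20%/5-day loss. Nominal is 2.5% per tail.

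| Loss | Mean rate 4: favouring / against drug | Mean rate 8: favouring / against drug |
|---|---|---|
| Treatment only | 6.0% / 0.9% | 7.8% / 0.6% |
| Run-In only | 0.8% / 6.1% | 0.6% / 8.2% |
| Equal | 2.4% / 2.5% | 2.4% / 2.3% |

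With observed hours as the denominator, each tail returns to about 2.5% in every case. Repeat runs agree to within a few tenths of a percentage point.

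**6. Precision with short wear.** For a Poisson count over d observed days, the SE of the scaled rate relative to full wear is sqrt(14/d): 3.74 at 1 day, 1.67 at 5, 1.41 at 7, 1.18 at 10.

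**7. Percentages.** If the scaling is applied as 14/days, the factor is 1.00 at 14 days, 14/13 = 1.08 at 13 and 14/10 = 1.40 at 10. A true 5% becomes 7% in a 10-day period.

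**The case against.** **The denominator may have been meant as days with CGM data.** Each period is planned at 14 days, so dividing by days does something only if days can vary. This reading is possible, but the plan does not state it, and the SMBG and Level 3 rates use the same wording although sensor wear has no bearing on them. Even on this reading, partly lost days still count in full.

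**The loss the documents themselves imply is small.** This stands. Placement on Day 1 affects both Run-In and Period 1, and the Period 2 removal falls about equally on both regimens. At the assumed times and rates the net schedule effect is at most about 5% of the difference (0.20/4.0), and less if hours before placement are treated as preceding the period.

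**The larger figures have no source in the documents.** This also stands: no passage gives a sensor-loss rate or shows that loss is one-sided. Under equal loss the false-positive rate is nominal. The simulation uses a paired t-test, not the planned mixed model. These figures show what the definition permits; they do not predict what will happen in this trial.

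**The percent-time wording is editorial.** Largely so: it does harm only if a period is not 14 days and the clause is applied arithmetically.

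**The remedy has its own costs.** Excluding a low-wear Run-In removes the baseline for both regimens. Scaling by hours assumes a roughly even event rate across the window, and on Day 14 of Period 2 the observed hours include the meal test. These are reasons to choose the rule carefully and to allow weighting instead of exclusion. They do not justify counting unobserved time as event-free.

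**Conclusion.** The concern holds. As written, both CGM event counts are understated by the share of the window without sensor data, and nothing in the plan corrects for it. The proportional understatement follows from the definition when loss is unrelated to events. Its size in this trial cannot be taken from the documents: the schedule alone contributes a few percent, while uneven loss of several days in a minority of participants could shift the primary difference by 7 to 14% under the assumptions shown. The direction is undetermined. Reading the denominator as days with CGM data would leave only partial-day loss. The scaling of the three percentages is redundant at 14 days and distorting at any other length if applied as 14/days. The plan should be changed because the fault sits in the primary endpoint and the repair is cheap.

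**What to change.** - **Two CGM event counts.** Define the rate, separately for Run-In and each treatment period, as events / observed in-window CGM hours x 196 (diurnal) or x 84 (nocturnal).
- **Wear rule.** Prespecify a minimum, for example half the window (98 diurnal or 42 nocturnal hours), which limits the Poisson SE to 1.41 times that of full wear, and report how many periods are excluded. Alternatively, keep every period and weight by observed hours. Fix the choice before the data are seen.
- **SMBG and Level 3 rates.** Keep days in the period as the denominator; these do not depend on the sensor.
- **Three percent-time endpoints.** Delete the 14-day normalization.

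The cost is a revision of endpoint and analysis wording. The CGM data are already downloaded after Run-In and at the end of each period, so no new visits or measurements are needed. The downside is that a few low-wear periods may be excluded or down-weighted; in a trial of at most 20 participants, weighting avoids losing a participant's baseline.

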### ***Secondary Endpoints***

The secondary endpoints include the following:

- Rate of Level 2 hypoglycemia, defined as number of distinct episodes of Level 2 hypoglycemia (SMBG glucose <54 mg/dL), divided by number of days for a given treatment period, then normalized to duration of 14 days.
- Rate of Level 3 hypoglycemia (severe hypoglycemia), defined as the number of severe events during each treatment period characterized by altered mental and/or physical functioning that requires assistance from another person for recovery, divided by number of days for a given treatment period, then normalized to duration of 14 days. This applies regardless of whether a patient actually receives external assistance. Since the categorization of a severe hypoglycemia event can be subjective, particularly in cases where severe neuroglycopenic symptoms/signs occurred and external assistance was needed but was not received, all potential qualifying severe hypoglycemia events will be adjudicated by the principal investigator.
- Percent diurnal time <54 mg/dL, defined as the percentage of CGM values <54 mg/dL during daytime hours (8am-10pm) within each treatment period, normalized to 14 days.
- The magnitude of postprandial hypoglycemia, defined as the glucose nadir as measured by fingerstick glucose occurring within 3 hours of standardized liquid meal consumption. The plasma glucose nadir obtained during avexitide plus standard of care (Treatment Periods 1 and 2) will be compared to during standard of care (Run-In). Particularly, the baseline-adjusted plasma glucose nadir will be calculated for each patient and evaluated.

Secondary endpoints will be analyzed in the same manner as the primary efficacy endpoint.

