## INVESTIGATIONAL PLAN

### Study Design

**Overview**—This is a Phase 2b, single center, open-label, cross-over study of avexitide injection in patients with surgically-induced severe, diet-refractory HH. Eligible participants must have a confirmed diagnosis of surgically-induced HH and demonstrate severe, diet refractory HH, as documented by presence of at least two severe hypoglycemia events from which at least one must be characterized by glucose <54 mg/dL as measured by CGM during the 14-day Run-in Period while adhering to medical nutritional therapy.

[figure not shown]
Eligible HH indications include hypoglycemia occurring after:

- Bariatric Surgery:
  - Roux-en-Y Gastric Bypass (RYGB) or Vertical Sleeve Gastrectomy (VSG)
- Upper-Gastrointestinal Surgery:
  - Gastrectomy, Esophagectomy, or Nissen Fundoplication

Provisionally eligible subjects will undergo a 14-day Run-In consisting of standard of care (SOC) treatment (medical nutrition therapy) with standardized mixed meal consumption and screening labs and collection of blood to test for anti-drug antibody (ADA) at the end of the 14-day SOC Run-In to confirm eligibility and establish a baseline within 90 days of randomization. Enrolled participants will be randomized to one of two 14-day avexitide dosing regimen orders (Figure 1). Doses are to be self-administered in the outpatient setting via subcutaneous (SC) injection. Throughout the study duration participants will continue to maintain SOC treatment following standard dietary guidelines for management of PBH and will be evaluated by blinded CGM, patient electronic diary (eDiary) and SMBG. At the end of Treatment Periods 1 and 2, participants will repeat baseline assessments with ADA and trough PK samples additionally drawn. At the end of Treatment Period 2, participants will return used and unused study drug vials during the safety follow-up visit.

**Study Duration**— Depending on when a patient completes the Run-In Period, the maximum anticipated time an individual patient will participate in the study will be ~120 days.

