## **STUDY POPULATION**

### **Inclusion Criteria**

Patients must meet all of the following inclusion criteria before study entry to be eligible for enrollment.

1. Able to understand the purpose and risks of the study; willing and able to adhere to scheduled visits, treatment plans, laboratory tests, procedures, and provide written informed consent
2. History of qualifying bariatric or upper-gastrointestinal surgery (RYGB, VSG, gastrectomy, esophagectomy, or Nissen fundoplication) at least 12 months prior to the start of Screening
3. Male or female, at least 18 years old (inclusive) at Visit 1 (Screening)
4. Body mass index (BMI) of up to 40 kg/m^2
5. Has stable body weight, i.e., not varying by >5% for at least 4 months prior to Visit 1 (Screening), as documented by the investigator
6. History of recurrent hypoglycemia refractory to bariatric dietary recommendations occurring after bariatric or upper-GI surgery, as documented in the medical record.
7. At least two severe hypoglycemia events from which at least one must be characterized by glucose <54 mg/dL as measured by CGM during the 14-day Run-in Period while adhering to medical nutritional therapy.
8. If female, must meet the following criteria:
  - a. Not breastfeeding or lactating
  - b. Negative urine pregnancy test result at Visit 4 (Screening) (not applicable to hysterectomized females); urine pregnancy test at Screening must be confirmed negative prior to randomization and dosing.
  - c. If of childbearing potential (including peri-menopausal women who have had a menstrual period within 1 year) must agree to use appropriate birth control (defined as a method which results in a low failure rate, i.e., less than 1% per year, when used consistently and correctly, such as implants, injectables, hormonal contraceptives, some intrauterine

contraceptive devices, sexual abstinence, tubal ligation or occlusion, or a vasectomized partner) during the entire duration of the study. Subjects must practice appropriate birth control as stated above for 4 weeks after the last dose of study drug.

- Nonchildbearing potential is defined as surgically sterile (documented hysterectomy, tubal ligation, or bilateral salpingo oophorectomy) or postmenopausal (defined as 12 months of spontaneous amenorrhea).
- 9. Has no clinically significant abnormal complete metabolic panel (CMP) as judged by the investigator. Note: CMP collected at Visit 4 unless assessed within 6 months prior to randomization.

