### **Dispensing and Administration of Study Drug**

Three kits of study drug (two containing 28 x 3mL vials and one containing 6 x 3mL vials of 90 mg/ml solution) will be dispensed by the Investigator on V4. Participants will be given written and oral instructions on how to store, draw up and safely administered study drug. The study drug will be administered as subcutaneous injections either once daily in the morning (90 mg QD), or twice daily (45 mg BID): once in the morning and the second daily dose approximately 12 hours later. During once daily dosing, the morning dosing will occur at least 60 minutes prior to the first morning meal. During twice daily dosing, the morning dosing will not be relative to the timing of the first meal of the day.

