### **Drug Accountability**

Drug accountability will be maintained by the principal investigator, who will ensure that a current record of investigational product disposition is maintained and that the investigational product is used only in accordance with the approved protocol.

Patients will be instructed to return all used and unused vials of study drug when they come to the clinic for the final study visit. Adherence with the prescribed regimen for each study drug will be estimated by counting the number of used and unused vials.

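### Level 3 events need judgement, and the plan does not mask study period or regimen from the adjudicator, so differences in judgement could enter the comparison with Run-In

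*Combined protocol and SAP*

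**What the plan says.** All references are to the combined protocol and SAP.

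- **The endpoint needs judgement.** Secondary Endpoints gives its reason for adjudicating as "Since the categorization of a severe hypoglycemia event can be subjective", and singles out cases in which the patient needed help and got none. Such cases count, because of the definition: "This applies regardless of whether a patient actually receives external assistance".
- **The safeguard.** The same section provides that "all potential qualifying severe hypoglycemia events will be adjudicated by the principal investigator". It mentions no second reader, no redaction, and no criteria beyond the definition.
- **The setting.** Study Design describes a "Phase 2b, single center, open-label, cross-over study of avexitide injection". Drug kits "will be dispensed by the Investigator on V4" (Dispensing and Administration of Study Drug), and "Drug accountability will be maintained by the principal investigator" (Drug Accountability). The only blinding described is that of the CGM device.
- **The comparison.** Secondary endpoints are analysed like the primary endpoint, which sets the two avexitide periods against Run-In. Run-In is untreated and always comes first.
- **Eligibility.** Inclusion criterion 7 requires "At least two severe hypoglycemia events from which at least one must be characterized by glucose <54 mg/dL as measured by CGM" during Run-In. Screening Procedures describes a review of Run-In events in which either a CGM reading below 54 mg/dL or a Level 3 event counts.

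**The concern.** When an outcome depends on judgement and the person classifying it knows the treatment, the threshold for calling an event severe can shift between periods without anyone intending it. Here the comparison of interest is avexitide against an untreated period that always comes first. Randomizing the order of the two regimens does not protect that comparison. If borderline events are upheld more readily in Run-In than on drug, the Level 3 rate falls even when the events themselves have not changed.

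For some patients there may be a second influence, because severe events in Run-In may bear on eligibility. Upholding a borderline Run-In event could then help a patient to qualify, and would also raise the baseline against which avexitide is judged.

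What is at stake is how far a reported reduction in the Level 3 rate can be attributed to the drug. The plan tests at a nominal 0.05 without multiplicity adjustment, so a significant Level 3 result would face no further statistical hurdle.

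**Working it through.** **Step 1. Is the adjudicator masked?** No sentence says that the adjudicator knows the period or regimen. The trial is open-label at one center, the investigator dispenses the drug, the principal investigator keeps the accountability records, and no masking of adjudication is described. Knowledge of period and regimen is therefore a presumption, but the natural one.

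**Step 2. Is there a figure to reproduce?** No. The documents give a cap of 20 participants (Number of Participants), but no Level 3 rate, share of borderline events, effect size or power. Everything below is illustration on assumed inputs.

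**Step 3. Apparent reduction from judgement alone.** Let u0 be the share of candidate events upheld in Run-In and u1 the share upheld on treatment, with the same underlying event rate in both. Then

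apparent reduction = 1 − u1/u0.

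With u0 = 0.9 and u1 = 0.7, this is 1 − 0.7/0.9 = 22%.

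Another way to judge plausible values is to suppose that a share b of the events upheld in Run-In are borderline, and that a share q of such events would be downgraded on treatment only. Then u1/u0 = 1 − bq, and the reduction is bq:

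- b = 0.25, q = 0.1: 2.5%
- b = 0.50, q = 0.2: 10%
- b = 0.75, q = 0.4: 30%

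This version models downgrading on treatment only. Upgrading in Run-In would add to it.

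**Step 4. Chance of a falsely significant reduction.** A simulation (10,000 runs) assumed 20 participants, no drug effect, gamma-Poisson candidate events with a between-subject coefficient of variation of 0.7, and a two-sided 5% paired t-test of one regimen against Run-In. The t-test simplifies the planned mixed model. Participants were not selected on Run-In events, so regression to the mean plays no part in these figures.

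| u0 | u1 | Apparent reduction | 1 candidate event per 14 days | 2 | 4 | 6 |
|---|---|---|---|---|---|---|
| 0.8 | 0.8 | 0% | 2.5% | 2.5% | 2.5% | 2.5% |
| 0.9 | 0.8 | 11% | 5% | 6% | 9% | 12% |
| 0.9 | 0.7 | 22% | 9% | 14% | 25% | 35% |
| 0.9 | 0.6 | 33% | 16% | 30% | 51% | 68% |
| 0.9 | 0.5 | 44% | 28% | 50% | 79% | 91% |

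With equal shares upheld, the error stays at the nominal one-tail level. A small shift in judgement raises it modestly. The large values need a large shift.

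**Step 5. Which endpoints are exposed?** Only the Level 3 rate passes through this adjudication. The primary endpoint and percent diurnal time below 54 mg/dL come from CGM, the Level 2 rate uses an SMBG threshold, and the meal-test endpoint is a fingerstick nadir.

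**The case against.** The case for leaving the plan alone has real substance. This is a small study whose dose rationale calls the work preliminary. It has a written definition of Level 3 and a single adjudicator for all periods, which gives some consistency. The objective endpoints are untouched. For 45 mg BID against 90 mg QD the order is randomized, so bias there has no obvious direction. All of this stands, and it limits the scope of the point. It does not supply masking for the comparison with Run-In.

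Several stronger readings are tempting, and the documents do not support them:

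- **A reader might infer that one person enrols every patient and therefore has a direct interest.** The sections on screening and randomization do not say who enrols.
- **A reader might infer a general incentive to call Run-In events severe.** Criterion 7 does not tie its severe events to Level 3, and Screening Procedures lets CGM readings below 54 mg/dL count. A patient might qualify without any Level 3 judgement, so the pressure may apply to some patients only.
- **A reader might rank Level 3 as the leading secondary endpoint.** The documents do not rank the secondary endpoints.
- **A reader might take the illustrative figures as an estimate of bias.** They show what is possible under assumed inputs, and nothing in the documents shows which row applies.

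It can also be objected that masking at one site with at most 20 participants will be imperfect, because the investigator may recognise a narrative. That is true, but partial masking is still better than none.

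**Conclusion.** The point holds as a gap in the method for one secondary endpoint. The plan acknowledges that classification can be subjective, gives it to an investigator in an open-label trial, and describes no masking of period or regimen. Followed as written, it lets differences in judgement between Run-In and treatment enter the Level 3 comparison.

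The size cannot be derived from the documents. On the assumptions shown, the apparent reduction runs from 2.5% to 44%. At 2 candidate events per 14 days, upholding 90% in Run-In and 70% on treatment raises the chance of a falsely significant reduction from 2.5% to 14%. The conclusion rests on the presumption that the adjudicator knows the period, and it concerns what could happen. It does not show that a Level 3 result would be wrong, and it casts no doubt on the primary endpoint. The change is worth making because it is cheap.

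**What to change.** Amend the Level 3 item under Secondary Endpoints as follows.

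1. For the endpoint, all potential Level 3 events from Run-In and both treatment periods are adjudicated in one batch after the last Visit 7.
2. The adjudicator works from eDiary records, which already capture symptoms, outcomes, corrective actions and assistance. Participant number, date, period, regimen and any reference to injections are removed, and the records are presented in random order.
3. Written criteria are fixed beforehand. They should also say which diary entries count as candidates, so that this selection does not bring knowledge of the period back in.
4. Any judgement of Run-In events made at Visit 4 serves eligibility only. No eligibility rule changes.
5. A sensitivity analysis counts all candidate events before adjudication in every period, and the share upheld is reported by period. A difference in that share is a warning and not proof, since the drug could also change how severe the candidate events are. Agreement between the Visit 4 judgement and the masked one would not serve instead: it covers Run-In only and cannot show downgrading on treatment.
6. The plan states that masking removes only the adjudicator's part of the bias. Participants know their treatment when they make diary entries, and selection on Run-In events can still produce regression to the mean.

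The cost is a few hours of data management for at most 20 participants. The same investigator can adjudicate, so no extra staff are needed. The downside is imperfect masking when a narrative is recognised.
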